10.9.3.6. Safety Management Plan

The process of SAE-Assessment is performed by Premier Research. In this context a trial specific 'Safety Management Plan' has to be prepared before first subject is recruited into the trial. The Safety Management Plan contains a detailed description of all procedures concerning the documentation and reporting of AEs, SAEs and SUSARs. Additionally, the Safety Management Plan describes the preparation of the Development Safety Update Report (DSUR), the Benefit-Risk-Assessment and the process of immediate actions to prevent the trial patients from immediate risks.

11. STATISTICS

No formal sample size calculation was done as this is an open-label extension trial. Up to 90 subjects will be included.

Data will be summarised using summary statistics. Continuous data will be presented with the number of observations, mean value, standard deviation, minimum, quartile 1, median, quartile 3 and maximum value. Categorical data will be presented as counts and percentages. The data will be presented by visit in tables and graphs. Individual subject data will be listed. Further details of all analyses will be given in the statistical analysis plan.

No “analysis sets” (intention to treat, per protocol, etc.) are defined. All subjects will be included in the analyses/data presentations (equivalent to a Full Analysis Set).

Only recorded data will be analysed/presented and any subjects who have missing data will only have observed data reported, with no imputation for missing data.

Interim cuts of data may be done on a yearly basis and as needed for regulatory purposes (e.g. 120-day safety update).

Data listings will show all recorded data.

Data from the trial is planned to be combined with relevant data from the IMPALA trial; these combined analyses will be reported separately.

11.1. Primary Endpoints

Number of AEs, SAEs, ADRs, and AEs leading to treatment discontinuation.

11.2. Secondary Endpoints

- (A-a)DO₂ during the trial
- 6MWD during the trial
- SGRQ total score during the trial
- Number of WLL and time to WLL during the trial.
- DLCO (% predicted), FEV₁ (% predicted), FVC (% predicted) during the trial
- PaO₂ and DSS during the trial
- Need for oxygen supplement therapy during the trial.
- Number of subjects not requiring treatment for aPAP and time off treatment after discontinuation of inhaled molgramostim.

11.3. Exploratory Endpoints

- GM-CSF levels before and 2 hours after dosing.

12. DIRECT ACCESS TO SOURCE DATA/DOCUMENTS

12.1. Access to Source Data and Documentation

The investigator should guarantee direct access to source documents for the monitor and auditors as well as for inspection by appropriate regulatory agencies, and the IEC/IRB, if required.

12.2. Subject Records and Source Data

The origin of source data in the trial will be specified for each trial site in a separate document.

It is the responsibility of the investigator to record essential information in the medical records in accordance with national regulations and requirements. The following information should be included as a minimum:

- A statement that the subject is in a clinical trial
- The identity of the trial e.g. Trial code
- Subject number
- That informed consent was obtained and the date
- Diagnosis
- Dates of all visits and telephone contacts with the subject during the trial period
- Any information relating to AEs
- All treatments and medications prescribed/administered (including dosage)
- Date of subject withdrawal
- Subject health service identification number.

The investigator is responsible for ensuring the accuracy, completeness, legibility and timeliness of the data recorded in the eCRFs. After each subject visit, the eCRF should be completed in a timely manner. Data reported in the eCRF that are derived from source documents should be consistent with the source documents or the discrepancies should be explained. Data recorded in the eCRFs will be monitored.

12.3. Study Monitoring

Regular monitoring visits will be performed according to International Conference on Harmonisation (ICH) Good Clinical Practice (GCP). Data will be evaluated for compliance with the protocol and accuracy in relation to source documents. In accordance with written standard operating procedures (SOP)s, the Clinical Research Associates (CRAs) will verify that the clinical trial is conducted and data are generated, documented and reported in compliance with the protocol, GCP and the applicable regulatory requirements.

12.4. Audits and Inspections

Authorised representatives of Savara, a regulatory authority, an IEC or an IRB may visit the site to perform audits or inspections, including source data verification. The purpose of a Savara audit or inspection is to systematically and independently examine all trial-related activities and documents to determine whether these activities were conducted, and data were recorded, analysed, and accurately reported according to the protocol, ICH GCP, and any applicable regulatory requirements. The investigator should contact Savara immediately if contacted by a regulatory agency about an inspection.

12.5. Independent Ethics Committee (IEC)/Institutional Review Board (IRB)

The investigator must obtain IEC or IRB approval for the investigation. Initial IEC/IRB approval, and all materials approved by the IEC/IRB for this trial including the patient consent form and recruitment materials must be maintained by the investigator and made available for inspection.

Any modification of the protocol must be documented in a protocol amendment and any amendment considered substantial requires approval/favorable opinion by the appropriate regulatory authority and IEC/IRB.

13. ETHICS

13.1. Ethics Review

This protocol and any amendments will be submitted to a properly constituted IEC/IRB, in accordance with the ICH guidelines, the applicable European Directives and local legal requirements, for approval/favorable opinion. An approval/favorable opinion must be obtained in writing before the first subject can be recruited.

13.2. Ethical Conduct of the Study

The trial will be conducted in compliance with the protocol, applicable regulatory requirements, ICH GCP and the ethical principles of the latest revision of the Declaration of Helsinki as adopted by the World Medical Association.

14. DATA HANDLING AND RECORD KEEPING

14.1. Data Management

Data management and handling of data will be conducted according to the trial specific Data Management Plan with ICH guidelines and SOPs.

An eCRF system, will be used to capture data from the trial. Data entry will be performed by the trial site personnel. Validation and data queries will be handled by qualified Contract Research Organisation (CRO) staff. The data will be subjected to validation according to a data validation plan in order to ensure accuracy in the collected eCRF data.

Changes to the data in the eCRF will be made at the site by delegated trial site personnel. The eCRF will have an audit trail with appropriate functionality for data capture, tracking and documentation of any queries or changes. Electronic signatures will be used to lock the data and identify the person entering or changing the data.

Before database closure a reconciliation will be performed between the SAEs entered in the safety database and the trial database. After database closure, the database will be exported as SAS® data sets.

Any deviations, i.e. discrepancies and additions from the process defined in the Data Management Plan, will be described in a trial specific Data Management Report.

14.1.1. Protocol Deviations

The instructions in the protocol must be followed. If deviations occur, the investigator must inform the CRA and the implications of the deviation must be reviewed and discussed. Deviations must be documented. In addition, deviations must be accompanied by a description of the deviation, the relevant dates (start and stop) and the action taken. Deviation reports and supporting documentation must be kept in the investigator's file and in the trial master file.

14.2. Inspection of Records

The Investigator agrees to allow the monitor to inspect the drug storage area, trial drug stocks, drug accountability records, subject charts and trial source documents, and other records relative to trial conduct.

14.3. Retention of Records

The investigator/institution should maintain essential documents (as defined in ICH E6 GCP, Section 8) as required by the applicable regulatory requirement(s). The investigator/institution should take measures to prevent accidental or premature destruction of the documents.

Essential documents should be retained according to applicable regulatory requirements of the country(ies) where the product is approved, and/or where the sponsor intends to apply for approval. If it becomes necessary for Savara or the Competent Authority to review any documentation relating to the trial, the Investigator must permit access to such records.

It is the responsibility of the sponsor to inform the investigator/institution in writing as to when the documents no longer need to be retained.

15. FINANCE AND INSURANCE

The sponsor must provide insurance or must indemnify (legal and financial coverage) the investigator/the institution against claims arising from the trial, except for claims that arise from malpractice, negligence or non-compliance with the protocol.

The compensation to the investigators for work performed under this protocol will be set out in separate clinical trial agreements with the investigators.

16. TRIAL ORGANISATION

The telephone numbers and fax numbers of relevant Sponsor staff are listed in the investigator site file.

The title, name, address and contact details of CROs, laboratories and other vendors are listed in [Appendix 3](#) Trial Organisation.

17. PUBLICATION POLICY

Information about this clinical trial will be publicly registered on the website www.clinicaltrials.gov before the first subject enters into the trial.

A Clinical Trial Report will be prepared according to the ICH Guideline for Structure and Content of Clinical Trial Reports (ICH E3).

All information supplied by the sponsor in connection with this trial will remain the sole property of the sponsor and is to be considered confidential information. No confidential information will be disclosed to others without obtaining prior written consent from the sponsor.

Savara is committed to data transparency by disclosing information from its research programs through presentations at scientific congresses and publication in peer-reviewed journals. Savara adheres to the International Committee of Medical Journal Editors (ICMJE) recommendations regarding authorship.

Draft manuscripts for joint publication will be prepared in collaboration between Savara, the coordinating Investigator and other Investigators, as appropriate depending on their contribution to the trial.

Investigators participating in this multicenter trial may publish data subsets from their individual institution only after publication of the primary manuscript. Written permission to publish must be obtained from the sponsor in advance. As some of the information regarding the IMP and development activities at the sponsor may be of a strictly confidential nature, the sponsor must be given a 30-day period to review and approve any publication manuscript prior to their submission to journals, meetings or conferences. Such a manuscript should always reference the primary publication of the entire trial.

The sponsor undertakes to publish the results in compliance with the joint position of the innovative pharmaceutical industry [Joint Position on the Disclosure of Clinical Trial Information via Clinical Trial Registries and Databases, available from http://clinicaltrials.ifpma.org/clinicaltrials/fileadmin/files/pdfs/EN/November_10_2009] for public disclosure of clinical trial results in a free, publicly accessible database, regardless of outcome, no later than one year after the medicinal product is first approved and is commercially available in any country.

19. APPENDICES

APPENDIX 1 LIST OF REVISIONS OF PROTOCOL

Table 5: Revisions of Protocol

Date	Version	Description of Document	Rationale for change
23-Oct-2017	1.0 This version was never submitted to any authorities	Final Protocol	NA
16-Nov-2017	2.0	Final Protocol, substantial amendment	NA
31-Jan-2018	3.0 This version only submitted in France and Denmark.	
Substantial Amendment 1 to the protocol:
 
The following updates have been made to the protocol:
 
Protocol synopsis:
 
 Detailed explanation of the possible treatment duration. 
Flow chart:
 
 IMP will not be administered at visit 7, which is marked in the flowchart in protocol version 2. This is an error and will not be applicable in any country. 
Section 10.8:
 
 It is clarified that CT scans only will be performed, if it is a part of clinical praxis. 
Section 10.8.5.2:
 
 It is clarified that CT scan isn't a part of the protocol, and should only be performed as part of clinical praxis, e.g. clinical deterioration 	
 Elaboration of treatment duration requested by the authorities in France and Denmark. Correction of an error. Clarification required by the French authorities. Clarification required by the French authorities.

Date	Version	Description of Document	Rationale for change
15-Mar-2018	Version 4.0 This version was only submitted in UK	
Substantial amendment 2 to the protocol: The following updates have been made to the protocol:
 
Protocol synopsis: Inclusion criterion 2: Clarification of inclusion criterion, including elaboration of sexual abstinence
 
Section 7.1 Inclusion criterion 2 Clarification of inclusion criterion, including elaboration of sexual abstinence
	
 • Clarification to ensure full compliance with CTFG guidance 2014, which is a UK requirement but applicable for all countries • Clarification to ensure full compliance with CTFG guidance 2014, which is a UK requirement but applicable for all countries

	
Version 5.0 Changes implemented for France and Denmark (Version 3.0) and UK (version 4.0) are made global in version 5.0 and applies to all countries in (version 5.0).
	
Substantial amendment 3 to the protocol: The following updates have been made to the protocol:
 
Protocol synopsis and flow chart: The first sentence in the note to Inclusion criterion 2 is deleted.
 
Exploratory endpoint added for GM-CSF levels before and 2 hours after dosing PK samples at visit 1-6 to be collected, only for patients in Italy. Note J is updated for patients in Italy: The visit should take place during the week on treatment and the dosing must be done at the clinic, in order to collect pre-dose PK. Clarification that spirometry and DLCO should be performed in accordance with European Respiratory Society/American Thoracic Society (ERS/ATS) guidance
 
Section 4.1: The sentence “consistent with findings from other rhGM CSF products” deleted. For updates on MOL-PAP-002: The US added as a country and planned number of randomized patients increased from 90 to 135. Latest DSMB was in April 2018 and not October 2017, with 96 randomized patients. The last visit reviewed is changed from visit 12 to visit 13 and FU is now 48 weeks instead of 36 weeks.
 
Section 4.2 Rationale for collection of PK samples for Italian patients added.
 
Section 5.3.3
	
 • Guidance text inadvertently inserted. This is not relevant for molgramostim. • Sponsor decision in order to better characterize systemic safety • Missing in previous versions • Changes in the MOL-PAP-002 trial implemented and updates found relevant for the section • Sponsor decision in order to better characterize systemic safety • Sponsor decision in order to better
--	--	--	--

Date	Version	Description of Document	Rationale for change
		
Exploratory endpoint added for GM-CSF levels before and 2 hours after dosing
 
Section 7.1 The first sentence in the note to Inclusion criterion 2 is deleted.
 
Section 9.5 A note for the Italy is inserted, to ensure the visits are scheduled in a week during treatment and the subject will administer the dose at the clinic, after collection of the pre-dose PK-sample.
 
Section 10.4.1: 6MWT instruction referral is added
 
Section 10.4.7: Spirometry should be performed according to ARA/ERS guidelines.
 
Section 10.7.2: Instructions for 6MWT is provided in Appendix 4.2 and not in a separate document.
 
Section 10.8.5: All laboratory results must be entered in the eCRF.
 
Section 10.8.5.1: Additional PK samples requested to be collected for Italian patients.
 
Section 11.3: Exploratory endpoint inserted.
 
Appendix 4.2: Instruction for 6MWT added.
	
characterize systemic safety
 
 • Guidance text inadvertently inserted. This is not relevant for molgramostim. • The note is added to ensure clarity in administration of IMP for the Italian subjects. • Missing in previous versions • Missing in previous versions • Missing in previous versions • Sponsor decision in order to better characterize systemic safety • Sponsor decision in order to better characterize systemic safety • Due to additional PK-sample collection • Missing in previous versions

APPENDIX 4 QUESTIONNAIRES

APPENDIX 4.1 BORG CR10 SCALE

0	Nothing at all	
0.3		
0.5	Extremely weak	Just noticeable
0.7		
1	Very weak	
1.5		
2	Weak	Light
2.5		
3	Moderate	
4		
5	Strong	Heavy
6		
7	Very strong	
8		
9		
10	Extremely strong	"Maximal"
11		
↖		
●	Absolute maximum	Highest possible

Borg CR10 Scale®
© Gunnar Borg, 1982, 1998, 2004
English

APPENDIX 4.2 TRIAL SPECIFIC GUIDELINE FOR THE 6MWT 6 MWT AND CR10 (BORG'S) DYSPNOEA SCALE

6MWT

The 6MWT should be conducted according to ATS/ERS technical standard (Field Walking Tests in Chronic Respiratory Disease – Eur Respir J 2014; 44:1428-1446).

The 6MWT should be performed on a flat, straight course with a hard surface with little pedestrian traffic

The walking course should be 30 m or more in length.

The end of the course should be marked such that they are easily visible to patients. The same course should be used at each visit.

The patient should sit at rest in a chair, located near the starting position, for at least 10 minutes before the test starts

The test should be completed with the subject breathing room air, if possible. If a patient is on chronic oxygen therapy and not able to complete the 6MWT on room air, an oxygen titration procedure will be conducted at screening. The procedure described in Appendix 4 should be followed. The same flow of oxygen should then be used at the subject's subsequent tests in the trial, unless a higher flow is required due to the subject's medical condition.

Patients should be encouraged every 60 seconds using standard phrases. Other words of encouragement and other nonverbal prompts should not be used.

If the patient stops walking during the test, the timer must not be stopped. The patient should be allowed to rest while sitting or standing, as they prefer. During the stop, standard encouragement should be given every 30 seconds. The time the patient stopped during the test, should be noted in the eCRF.

If SpO₂ is < 80% then the test should be stopped

Two 6MWTs should be performed (due to the learning effect on the test), and the result from the test with the longest distance walked should be recorded. If the subject is not able to complete more than one test due to exhaustion or adverse events, this should be noted on the worksheet. There must be at least 30 minutes between the two tests.

The total distance walked should be recorded

SpO₂ should be measured using a pulse oximeter continuously during the test. The start value and the lowest value during 6MWT should be recorded

Start heart rate and end heart rate should also be recorded

Use the study-specific worksheet for documenting values, which is provided by sponsor to the sites.

The results from the 6MWT with the longest distance walked and the related SpO₂ and CR10 (Borg) scale results should be entered in the eCRF.

Standard encouragement during a 6-minute walk test

1 min: You are doing well. You have 5 minutes to go.

2 min: Keep up the good work. You have 4 minutes to go.

3 min: You are doing well. You are halfway.

4 min: Keep up the good work. You have only 2 minutes left.

5 min: You are doing well. You have only 1 minute to go.

6 min: Please stop where you are.

If the patient stops during the test, every 30 s once SpO₂ is $\geq 85\%$ the following standard phrase should be use:

“Please resume walking whenever you feel able.”

CR10 Scale/Borg’s dyspnoea scale

The CR10 (Borg’s) scale for dyspnoea provided by Savara should be rated before and after the 6MWT. Let the patient read the instruction before rating their dyspnoea on the CR10 scale. Standard instructions for the CR10 (Borg scale) will be provided in local language.

If possible, the test should be conducted using the same oxygen flow level as was used in IMPALA. If a subject has started chronic oxygen therapy after being enrolled in IMPALA, an oxygen titration procedure should be conducted as described below.

This procedure only applies for patients on chronic oxygen supplementation at screening:

The patient will perform an O₂ titration procedure at Screening to determine the amount of supplemental oxygen that the patient needs to complete the 6MWT without developing O₂ desaturation. This oxygen flow rate will represent the patient’s baseline O₂ flow rate for all subsequent 6MWT procedures for this study.

Equipment and supplies:

The equipment and supplies needed for the Oxygen Titration Procedure are the same as those needed for the 6MWT. Verify that your oxygen flow meter is accurate (to within 0.5 liters per minute).

Patient safety:

The safety precautions for the Oxygen titration procedure at the screening visit are same as required for the 6MWT.

Procedure:

Step 1: Resting O₂ Titration

Attach the pulse oximeter. Set it to alarm when SpO₂ falls below 83%.

Instruct the patient to sit still and not chat.

Discontinue supplemental oxygen. Start the timer for 10 min. If resting SpO₂ decreases to below 83% during the 10 minutes resting period, then start supplemental oxygen at 2 L/min. If resting SpO₂ again decreases below 83% during the next 10 minutes, then increase O₂ to 4 L/min. If resting SpO₂ remains below 83% during the next 10 minutes, then increase OR2R to 6 L/min. If resting SpO₂ remains below 83% during the 10 minutes at rest on 6 L/min of supplemental oxygen, the patient should not conduct the 6MWT.

The lowest oxygen flow for which a patient can maintain a resting SpO₂ >83% for 10 minutes will be the initial flow rate for the Walking portion of the O₂ titration procedure.

Step 2: Walking O₂ Titration

Before starting the exercise evaluation, the patient should be seated and resting for at least 10 minutes on the oxygen flow rate determined during the resting O₂ titration procedure.

Follow the 6MWT procedures, starting at the O₂ flow rate established in the resting O₂ titration. Start the timer when the patient begins walking.

If the patient's SpO₂ decreases to below 83%, stop the walk and increase supplemental oxygen by 2 L/min. The patient should then be seated and allowed to rest for 5 min. The Walking O₂ titration procedure should then be repeated at the higher O₂ flow rate. If the patient's SpO₂ decreases to below 83% at any time, repeat the Walking titration. If during the 6MWT on 6 L/min of oxygen SpO₂ drops below 83% (sustained for at least 30 seconds), stop the walk. If the patient has not completed a distance of >150 meters, the patient should not conduct the 6MWT

The lowest oxygen flow on which a patient can complete the 6MWT without developing a SpO₂ below 83% will be the patient's O₂ flow for all subsequent 6MWT conducted during the course of the study.

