- ^d Only applicable if assessment is done according to clinical practice or medical need, e.g. in case of a clinical deterioration. If done, results will be recorded
- ^e Capillary sampling for blood gas analysis may be used instead of an arterial blood gas sample at sites that routinely use this method.
- ^f DLCO, FEV₁, and FVC (absolute values and % of predicted values).
- ^g 6MWT includes assessment of SpO₂ and Borg CR10 score for dyspnoea before, during (SpO₂) and after (Borg) the test. If the subjects used supplemental O₂ during the procedure in IMPALA, the same O₂ flow will be used at the subsequent tests in this trial, if possible.
- ^h Haematology and clinical chemistry
- ⁱ For Italy only: Patients will have their visits scheduled for an on-treatment week within the allowed window of +/- 4 weeks. The first sample must be taken just prior to inhalation of molgramostim. The 2nd sample must be taken 2 hours post dosing, (+/- 10 minutes). See Section [10.8.5.1](#)
- ^j Trial drug is dispensed to subjects who require treatment according to investigator's discretion. **For Italy only:** The visit should take place in during the week on treatment. On the day of dosing, the subjects will do the nebulization at the clinic, in order to collect pre-dose PK sample.
- ^k Diary card to collect safety information to be given to the subject and collected at the next visit. The subject will be asked to record any AEs they have experienced, enter dates for pregnancy tests taken at home (if applicable) and dates for changing of the nebuliser mouthpiece in the subject diary.
- ^l If the planned trial termination has been declared since the subject's last visit in the trial, the subject will leave the trial.

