If possible, the 6MWT should be conducted using room air. If a subject is on long-term oxygen therapy, oxygen should be given at their standard flow rate and held constant throughout the test. The tests conducted should be performed using the same oxygen conditions that were used in IMPALA, if possible.

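### For a subject who starts long-term oxygen after joining IMPALA and cannot complete the walk on room air, the protocol sets the walk-test oxygen flow by rules that cannot all be followed

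*Protocol*

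**What the plan says.** **Protocol section 10.7.2** starts from room air if possible. For long-term oxygen users it continues: "If a subject is on long-term oxygen therapy, oxygen should be given at their standard flow rate and held constant throughout the test". It does not mention titration. It then adds: "The tests conducted should be performed using the same oxygen conditions that were used in IMPALA, if possible". For the trial-specific instructions it refers the site to Appendix 4.2.

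**Protocol Table 1, note g** covers subjects who used supplemental oxygen for the walk in IMPALA. For them the same "flow will be used at the subsequent tests in this trial, if possible". It says nothing about oxygen started later.

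**Protocol Appendix 4.2** makes four statements that bear on the flow.
- Its general instructions also start from room air. A chronic oxygen user who is "not able to complete the 6MWT on room air, an oxygen titration procedure will be conducted at screening". The resulting flow is kept for later tests, with an exception if the subject's condition calls for more.
- It asks for the IMPALA flow where possible, and then says: "If a subject has started chronic oxygen therapy after being enrolled in IMPALA, an oxygen titration procedure should be conducted as described below".
- The line that follows reads: "This procedure only applies for patients on chronic oxygen supplementation at screening".
- The titration steps end by making the lowest adequate flow the subject's flow "for all subsequent 6MWT conducted during the course of the study". No exception is given there.

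**Schedule.** Table 1 has Visit 1 (Baseline) to Visit 7, a follow-up call and unscheduled visits. It has no screening visit, and neither its rows nor its notes assign titration to a visit.

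**SAP section 7.2.2 and the list of tables** summarise distance, Borg and SpO2 by visit, with change from baseline, using the longer walk at each visit. Oxygen flow and oxygen use during the walk appear only in a listing.

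**The concern.** Walking distance, exertional breathlessness and desaturation all depend on the oxygen given during the test. If two sites can each follow the protocol and set different flows for similar subjects, or one site can set different flows for one subject at successive visits, a change from baseline mixes a change in disease with a change in test conditions.

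The SAP foresees oxygen being started during the trial: section 7.2.7 has a category for oxygen begun after baseline. Subjects who start oxygen may well be those who are worsening. For the other oxygen-sensitive endpoints the SAP has a rule: visits on supplemental oxygen are left out of the (A-a)DO2 summary (section 7.2.1) and the DSS summaries (section 7.2.6). The 6MWT summaries have no rule of any kind on oxygen.

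**Working it through.** No arithmetic applies. The plan gives no sample size calculation, no SD for 6MWD, no count of oxygen users and no effect of flow on distance. The check is whether the stated rules can be followed together.

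**Step 1. Fix the subject.** Take a subject who walked on room air in IMPALA, later starts chronic oxygen, and cannot complete the walk on room air. Room air where possible is common to section 10.7.2 and Appendix 4.2, so it is not a point of conflict. The request for IMPALA conditions is also qualified by possibility, and this subject cannot meet it.

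**Step 2. Standard flow or titrated flow.** Section 10.7.2 gives the subject the standard flow rate. Appendix 4.2 sends a subject who started oxygen after IMPALA enrolment to titration. The titration begins with oxygen discontinued and rises in steps of 2 L/min to 6 L/min, so as written it can end at 0, 2, 4 or 6 L/min. Nothing makes that result equal to the standard flow.

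**Step 3. Does the titration apply?** The appendix sentence requiring titration (A) is followed by the line limiting it to patients on oxygen at screening (B). Screening is not defined for this trial, so both possible meanings are tried.

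| Oxygen started | Screening = IMPALA screening | Screening = Visit 1 of this trial |
|---|---|---|
| After IMPALA enrolment, before Visit 1 | A requires it, B excludes it | A requires it, B allows it |
| After Visit 1 | A requires it, B excludes it | A requires it, B excludes it |

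A and B agree in only one of the four cells. For oxygen started after Visit 1 they disagree on either meaning. In the agreeing cell the difference between standard and titrated flow from Step 2 remains.

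**Step 4. May the flow change later?** The appendix's general instructions allow a higher flow if the subject's condition requires it. The closing line of the titration steps fixes the flow for every later test and gives no exception.

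**Step 5. Does the analysis absorb the difference?** It does not. SAP section 7.2.2 selects the longer walk with no condition on flow, and the change-from-baseline tables carry no oxygen restriction. Section 10.7.2 does have the flow recorded where applicable, so differences can be identified from data already collected.

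**The case against.** **A workable order can be read into the text.** Section 10.7.2 points to Appendix 4.2 for detail, and the appendix has a sentence for exactly this subject. A sensible site could try room air, then the IMPALA flow, then titrate. This narrows the problem. But section 10.7.2 does not say that the appendix overrides its own standard-flow sentence, and the appendix restricts its titration instruction in the next line.

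**Screening looks like wording carried over from another protocol and may simply mean Baseline.** That is plausible, and it settles the appendix's internal clash for anyone already on oxygen at Visit 1. It does not help a subject who starts afterwards. A subject who started oxygen during IMPALA may also already have an IMPALA walk flow to use.

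**The allowance for a higher flow may be a general qualifier on the fixed flow.** This is a fair reading, and it makes Step 4 the weakest part of the point. The two statements still need one wording.

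**Stronger readings that the documents do not support.**
- A reader might list room air, prescribed flow and titrated flow as three rival rules. Room air where possible is a shared first step, and a titration can itself end at 0 L/min.
- A reader might count Table 1 note g as a further conflict. It applies only to subjects who used oxygen in IMPALA.
- A reader might picture one patient walked at different flows by different sites. Nothing in the documents has a patient tested at several sites.

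**The consequence is modest.** The endpoint is secondary and descriptive in an uncontrolled extension. A subject whose baseline walk was on room air and whose later walks are on oxygen is not comparable with baseline under any single flow rule. All of this stands, and it is why the remedy needs an analysis part as well as a wording part.

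**Conclusion.** The inconsistency is real and in the current text. For a subject who starts chronic oxygen after IMPALA enrolment and cannot complete the walk on room air, section 10.7.2 and Appendix 4.2 name different flows. The appendix both requires and restricts titration by reference to a visit that Table 1 does not contain. The clearest case is oxygen started after Visit 1, where no meaning of screening removes the clash.

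The number affected is not given and may be small; the SAP reports 60 subjects enrolled in all. A reader might infer that everyone who started oxygen after IMPALA enrolment was walked at an uncertain flow, or that the exercise results as a whole are unreliable. The documents support neither. Some of these subjects can walk on room air or already have an IMPALA flow, and no size of effect on distance can be derived.

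What follows is that 6MWD, Borg and SpO2 for this subset may not be comparable across visits and sites. No error rate is at stake, and the primary safety objective is untouched. The conclusion assumes that at least one such subject exists and that sites had no other written instruction resolving the conflict.

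**What to change.** **Protocol.** Reconcile section 10.7.2 and Appendix 4.2 into one rule for walk-test oxygen. It should state whether a subject who starts oxygen after IMPALA enrolment is titrated or uses the standard flow, name a visit in Table 1 at which any titration takes place, and say whether the flow may change afterwards. The choice of rule is the sponsor's. The cost is wording and a site memo, plus an added assessment if the rule chosen places titration at a visit that does not now have it.

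**SAP.** The trial was stopped early, treatment was to continue only until the end of 2020, and SAP version 3.0 is dated 21 January 2021. Rewording cannot change walks already done. For these, flag each visit where the recorded oxygen flow for the analysed walk differs from the baseline flow, counting room air as a flow of zero. Then show the 6MWD, Borg and SpO2 summaries and their changes from baseline with and without the flagged visits. Where the baseline walk comes from IMPALA, its oxygen flow must be brought across with it.

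The cost is some extra tabulation and smaller numbers in the restricted summary. That summary may tend to drop subjects who worsened, so it should stand beside the full one and not replace it.
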